6.2.1 Medical History and Physical Examination

A medical history must be obtained and physical exam performed during the Pre-treatment Assessment to establish baseline medical condition(s) ([Section 6.2](#)). Medical history includes clinically significant diseases, history of cancer (including date of diagnosis, location of disease, stage, grade, biopsies, resections, prior cancer therapies and procedures), and selected medications (anti-neoplastic agents, blood products, soy products, antimicrobials, and G-CSF) used by the patient within 28 days prior to protocol therapy (genistein/placebo).

A full physical examination will be performed at the Pre-treatment Assessment and Day 1 of each cycle ([Sections 6.2](#) and [6.3](#)). Physical examinations will include examination of the following body systems: general appearance/constitution (including height and body weight), skin, neck, HEENT (head, ears, eyes, nose and throat), cardiovascular system (auscultation of heart sounds), lungs/chest (auscultation of lung fields), abdomen palpation, genitourinary system (auscultation of bowel sounds), lymph nodes, extremities, and nervous system.

An abbreviated, symptom-directed physical exam will be performed at all other visits ([Section 6.3](#)). This must also be conducted in such a way to assess for incidence of secondary conditions listed as endpoints (i.e., infection, mucositis, etc.) In addition, any clinically significant abnormal finding which was not noted at the baseline assessment must be reported as an AE, provided it also meets the reporting criteria in [Section 9](#).

Baseline conditions and AEs must be reported as diagnoses, when possible. Laboratory value abnormalities present at the time of enrollment must be reported as baseline conditions according to their CTCAE classifications. The baseline onset and severity of all grades of all target AEs defined in [Section 6.2](#) must be reported, as well as any other

non-target baseline condition if its severity is greater than or equal to grade 3 ([Section 9.1.8](#)). The outcome of baseline conditions and resolution dates, when applicable, must be reported at the end of the follow-up period.

6.3 Treatment Phase Assessments (Cycles 1 – 4)

Investigators should maintain good clinical practice and perform standard of care assessments and procedures per local institutional guidelines. In addition, the following list of study-specific assessments must be performed once a patient enters the Treatment Phase. All visits and assessments must be completed within \pm 72 hours of the milestone date unless otherwise specified.

- The following will be performed for the purposes of assessing clinically significant AEs. AEs found prior to the first study supplement dose must be reported as baseline conditions. See [Section 9](#) and the Procedure Manual for more information about AE reporting.
 - Chemistry/metabolic liver function labs on Day 1 of each cycle: must include serum creatinine, total bilirubin, AST, and ALT (Procedure Manual)
 - CBC with differential on Day 1 of Cycles 2, 3, and 4, and at weekly visits: must include hemoglobin, hematocrit, platelet count, total white blood cell count and automated white blood cell differential (manual differential if automated not available) (Procedure Manual). See below for additional requirements for ANC reporting.
 - Full physical exam on Day 1 of each cycle and a symptom-directed physical exam at each of the weekly visits ([Section 6.2.1](#))
 - The Pre-treatment and Cycle 1 Day 1 physical exams may be combined performed \leq 72 hrs. prior to Cycle 1 Day 1.
 - Subjects receiving vincristine must be assessed for vincristine toxicity in the form of peripheral motor neuropathy.
 - Audiograms for subjects receiving a platinum-based chemotherapy agent at 0 - 4 days prior to Day 1 of Cycles 2, 3, 4, and 0 - 4 days prior to the last day of Cycle 4. Assess hearing impairment and tinnitus.
- ANCs must be obtained as follows:
 - The ANC must include both neutrophils and bands. The following equation is recommended:
$$\text{ANC} = \text{WBC} \times 1000 (\% \text{ Neutrophils} + \% \text{ Bands})$$
 - Obtain on Day 1 of Cycles 2, 3, 4 and at weekly visits

- Once ANC levels begin to decrease, ANC must be determined at least twice weekly (≤ 96 hours between blood collection) until ANC recovers to ≥ 500 cells/ μ L, then switch to weekly testing in the following situations:
 - If nadir is < 500 cells/ μ L, begin once ANC ≥ 500 cells/ μ L, OR
 - If nadir is ≥ 500 cells/ μ L, begin once ANC has increased by 50% above nadir
- If ANC is < 500 cells/ μ L at any point after beginning weekly testing, resume twice weekly testing until ANC ≥ 500 cells/ μ L.
- ANC will be obtained daily during any admission for febrile neutropenia.
- All ANC values will be reported.
- Serum CRP, homocysteine, and ESR: Report raw data collected on Day 1 of Cycles 2, 3, 4, and the last day of Cycle 4
- Cytokine Panel and Isoflavone Panels: Draw and process specimen per the Procedure Manual on Day 1 of Cycles 1, 2, 3, 4, and the last day of Cycle 4
- Weight and height on Day 1 of each cycle
- The following **target AEs** must be assessed and the maximum grade reported for each cycle in addition to standard AE/SAE reporting ([Section 9](#)):
 - Neutropenia
 - Febrile neutropenia, with maximum associated temperature per cycle
 - Fever, including number of days per cycle, for temperatures $> 101.5^{\circ}$ F, or $> 100^{\circ}$ F more than once in a 24-hour period (report maximum temperature)
 - Infections and Infestations: Maximum grade for any AE listed in this CTCAE category. Infections meeting the AE reporting threshold must be listed individually.
 - Oral mucositis
 - Tinnitus (subjects receiving platinum-based chemotherapy only)
 - Hearing impairment (subjects receiving platinum-based chemotherapy only)
 - Peripheral motor neuropathy (subjects receiving vincristine only)
- Report per cycle:
 - Study supplement:
 - Total number of tablets taken

- Subject compliance with study medication dosing as determined by self-reported administration reports and supplement reconciliation
- Reason for dose change, if applicable. Any AE(s) precipitating a dose reduction must be reported even the minimum AE reporting threshold is not otherwise met ([Section 9.2](#)).
- Anti-neoplastic treatment delay(s):
 - Total number of days delayed from planned schedule
 - Cause for delay: AE, or reason other than AE
- Anti-neoplastic agent dose reduction(s):
 - Delayed agent(s)
 - Planned dose(s)
 - Actual dose(s)
 - Cause for dose change: AE, or reason other than AE
- All unplanned or prolonged hospitalizations due to (an) AE(s) ([Section 9.1.9](#)):
 - Date of admission or start of prolongation and discharge date
 - Causes/diagnoses precipitating hospitalization or prolonged hospitalization
- Concomitant medication review at each scheduled visit for the following:
 - Soy-based products: Product, dates of use. Reporting is limited to the soy-containing products described in [Section 4.8.1](#) and the patient handout in the Procedure Manual.
 - Antimicrobials: type (antibiotic, antifungal, antiviral, other); route of administration (IV, oral, other); dates of use; AE(s) precipitating use, prophylactic use, or the treatment of a presumed/known infection
 - Blood product transfusions: dates of use, blood product type (platelets, red blood cells, other), and indication ([Section 4.8.2](#))
 - G-CSF: Number of days per cycle that G-CSF was administered, primary or secondary use (planned before the cycle began or in response to prolonged neutropenia, respectively)
- Date of disease recurrence or progression, description of recurrence/progression, and site(s) of disease
- Date of secondary malignancy diagnosis, description of secondary malignancy, and site(s) of disease

- Date of death due to any cause, and description of clinical scenario surrounding the subject's death.

The procedures and assessments schedule is summarized on the Roadmaps in the Procedure Manual appendices.

Day 8 assessments must be repeated at intervening/additional weekly visits resulting from an anti-neoplastic therapy treatment delay or any other factors that causes the prolongation of a course.

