7 EVALUATION CRITERIA

7.1 Primary Endpoint

The primary endpoint of this clinical trial is the average day of neutrophil count recovery following myelosuppressive chemotherapy. Neutropenia will be defined as ANC < 500 cells/ μ l (grade 4 neutropenia per [CTCAE](#)), and the “day of recovery” for each subject during each cycle of chemotherapy will be defined as the first post-nadir day of each cycle that the ANC is \geq 500 cells/ μ l (i.e. \leq grade 3). For example, if the ANC is 400 cells/ μ l on Day 12 and 600 cells/ μ l on Day 14, then the day of recovery will be Day 14. For subjects whose ANC nadir is \geq 500 cells/ μ l, the day of recovery will be the day of the first ANC after their lowest ANC is obtained.

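### Recovery day is dated to a draw whose spacing depends on febrile-neutropenia admission, so any treatment difference in admissions shifts both co-primary comparisons

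*Combined protocol and SAP*

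**What the plan says.** Section 6.3 sets the sampling. "Once ANC levels begin to decrease, ANC must be determined at least twice weekly", with no more than 96 hours between draws, until recovery. It then adds: "ANC will be obtained daily during any admission for febrile neutropenia". Nothing restricts the endpoint to scheduled draws: "All ANC values will be reported".

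Section 7.1 dates recovery in each cycle to "the first post-nadir day of each cycle that the ANC is" at or above 500 cells/µl. Its example has an ANC of 400 on Day 12 and 600 on Day 14, and "then the day of recovery will be Day 14", so the later draw date stands and the whole gap enters the endpoint. Where the nadir never falls below 500, "the day of recovery will be the day of the first ANC after their lowest ANC is obtained", which again depends on when the next draw happens.

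Section 8.1 builds both co-primary endpoints from these recorded days: the mean over Cycles 1 and 2 compared between arms, and the genistein-minus-placebo difference within subjects. Section 7.2 lists unplanned hospitalization as a secondary endpoint. Sections 7.1, 8.1, 8.2 and 8.4 contain no common sampling grid, interpolation, interval-censored method or sensitivity analysis for unequal draw spacing.

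**The concern.** How late a recovery is recorded depends on whether the subject was admitted. Admission happens after randomization, follows from neutropenia with fever, and is itself a trial outcome that treatment may change. Randomization and blinding do not balance a measurement error that arises this way. Section 1.2.1 describes inpatient treatment continuing until febrile neutropenia resolves, so the daily draws will often cover the day of recovery.

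At stake is the primary effect estimate of a pilot planned around a 3-day difference with about 80% power. If the treatments lead to different admission rates, part of the recorded difference reflects draw spacing and not neutrophil recovery.

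**Working it through.** **The plan's own figure.** Section 8.2 states about 80% power with 22 subjects per group, Poisson means of 16.25 and 13.25, and a one-sided 5% Mann-Whitney-Wilcoxon test. In 20,000 simulated trials, power was 79.7% with continuity correction and 80.1% without, so the figure reproduces. It treats recovery day as observed with no sampling delay.

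**Delay caused by a gap.** Work in whole days and assume that the timing of draws is unrelated to the true recovery day. A gap of g days then adds 0, 1, …, g−1 days with equal probability, a mean of (g−1)/2.

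- Daily draws (g = 1): 0.
- Alternating 3- and 4-day gaps: (3/7)(1) + (4/7)(1.5) = 9/7 = 1.29 days (simulated 1.28).
- 96-hour gaps (g = 4): 1.5 days (simulated 1.50).
- Three draws a week (gaps 2, 2, 3): (4/7)(0.5) + (3/7)(1) = 5/7 = 0.71 day.

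**Bias.** Let D be the mean delay in a non-admitted cycle, and let p(P) and p(G) be the shares of placebo and genistein cycles sampled daily through recovery. Then

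recorded difference = true difference − [p(P) − p(G)] × D.

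The admission rates below are assumptions. The true difference is 3.0 days. Power uses the plan's model, one Poisson recovery day per subject, with admission independent of recovery day.

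| Admitted, placebo vs genistein | 3/4-day grid: formula / simulated / power | 96 h grid: formula / simulated / power |
|---|---|---|
| 40% vs 40% | 3.00 / 3.02 / 77% | 3.00 / 3.01 / 77% |
| 40% vs 30% | 2.87 / 2.89 / 74% | 2.85 / 2.85 / 73% |
| 40% vs 20% | 2.74 / 2.75 / 70% | 2.70 / 2.71 / 69% |
| 50% vs 20% | 2.61 / 2.62 / 67% | 2.55 / 2.55 / 64% |
| 60% vs 20% | 2.49 / 2.48 / 63% | 2.40 / 2.41 / 60% |
| 20% vs 40% | 3.26 / 3.24 / 83% | 3.30 / 3.31 / 84% |

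**Admission driven by duration.** Suppose instead that admission risk accrues at an assumed 5, 10 or 20% per neutropenic day after an assumed Day 9 onset. Admission is then 29% vs 19%, 48% vs 32% or 69% vs 50% (placebo vs genistein). On the 3/4-day grid the recorded difference is 2.86, 2.79 or 2.75 days, and power stays at about 77 to 78%.

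**No true effect.** On the 3/4-day grid, 40% vs 20% admitted gives a spurious −0.25 day and a type I error of about 3%. The reverse, 20% vs 40%, gives +0.26 day and about 7%.

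**Check of the remedy.** For true recovery day T and gap g, the first draw at or above 500 falls on average at T + (g−1)/2. The midpoint is g/2 earlier, so its mean is T − 0.5 for every g, and the dependence on draw spacing cancels. Simulation agrees: 3.00 to 3.01 days under the midpoint rule. One common twice-weekly or 96-hour grid for every cycle gives 3.0 days and about 77% power whatever the admission rates.

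**The case against.** A reader might infer that the plan will understate genistein's benefit. The documents do not support that as a flat statement. They give no admission rates, and Section 1.1 hypothesizes fewer short-term side effects in general, not fewer admissions. Shorter neutropenia would plausibly reduce admissions, but that is an inference. With equal admission shares there is no bias, and with more admissions on genistein the benefit is overstated.

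The size also rests on assumptions that mostly enlarge it. Twice weekly with a 96-hour limit is a minimum; at three draws a week the delay falls to about 0.7 day. The calculation takes daily sampling to last until recovery in every admitted cycle, and discharge before the ANC reaches 500 would shrink the effect. Nor can a large loss of power be assumed: when admission follows duration of neutropenia, almost none is lost. In the hypothesized direction the error is conservative. This is a pilot that aims at estimation, all ANC values are kept, and the Procedure Manual, which holds the detailed schedule, was not available and might set a tighter one.

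These points limit the size and make the direction conditional. They do not remove the mechanism. The repeated-measures models in Section 8.4 use the actual ANC values but do not correct recovery day, and a remedy chosen after unblinding would look data-driven.

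**Conclusion.** The concern holds in conditional form. Given the sampling rules in Section 6.3 and the dating rule in Section 7.1, non-admitted cycles are recorded up to about 1.3 to 1.5 days later on average for the same true course. Each co-primary comparison is biased by roughly the difference in admission share times that delay, toward or away from a benefit according to which treatment has more admissions.

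For assumed falls of 10 to 30 points on genistein, a true 3.0-day effect is recorded as about 2.9 to 2.6 days. Against 77% at equal admission, power ranges from almost unchanged (duration-driven admission) to about 64 to 67% (50% vs 20%, independent admission). The bias cannot exceed about 1.5 days, and reaches that only if every cycle on one treatment is admitted and none on the other. The point is modest but worth settling before unblinding, because it affects the primary endpoint and the data needed to remove it are already collected.

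**What to change.** Amend the derivation in Section 7.1:

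- **Nadir below 500:** take recovery day as the midpoint between the last ANC below 500 at or after the nadir (the nadir draw itself counts) and the first ANC at or above 500. Alternatively, analyze recovery as interval-censored between those two draws.
- **Nadir at or above 500:** no value below 500 exists, so the midpoint is undefined. Keep the current rule, but apply it to draws thinned to a pre-specified twice-weekly grid, with or without admission. Section 6.3 fixes no second weekly draw day, so the thinning rule must be written out, including whether the nadir is classified from all draws or from the thinned ones.
- **Sensitivity analysis:** report the current first-observed-day definition using all draws.

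The cost is a slightly less simple definition and some added derivation text. It needs no extra draws and no change to inpatient monitoring.

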8 STATISTICAL CONSIDERATIONS

8.1 Study Design

This is a multi-center, randomized, double-blind, placebo-controlled, stratified, two-arm trial with a cross-over component which results in both a between-group comparison (A vs B for Cycles 1 and 2 data) and a crossover within group difference comparison (genistein cycles minus placebo cycles data). Patterns of ANCs over time will be estimated and average day of recovery over the two cycles will be the primary comparison. Neutropenia is defined in [Section 7.1](#). For each subject, two co-primary endpoints will be estimated; a) the average day to recovery during Cycles 1 and 2, and b) the difference in the average days during genistein cycles and the average days during placebo cycles.

In addition, the study is designed to capture other clinically-relevant short-term side effects of therapy that appear to be reduced by genistein supplementation. Secondary endpoints are listed in [Section 7.2](#).

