8.2 Sample Size and Accrual

This pilot study is designed to obtain preliminary data to describe the overall pattern of ANC over time during myelosuppressive chemotherapy, assess neutropenia, and to determine whether the data support a decrease in time to recovery of 3 days for the genistein group compared to placebo. Target sample size for this pilot study was based upon results from a chart review performed at UVA which found that the mean day of recovery for pediatric cancer patients receiving myelosuppressive chemotherapy was day 16.25. Group sample sizes of 22 eligible subjects per group achieves approximately 80% power to detect a difference of 3 days with a 5% one-sided Mann-Whitney-Wilcoxon Test. These results were based on 3000 Monte Carlo samples assuming a null Poisson (mean 16.25) distribution and an alternative Poisson (mean 13.25) distribution. ANC determination and neutropenia are defined in Sections 6.3 and 7.1. Adjusting for a 10% ineligibility/drop-out rate, approximately 49 - 50 subjects may need to be accrued to the study.

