8.3 Stratification Factors/ Randomization

Stratification will be based on the length of chemotherapy cycles, between 14-day (i.e. Ewing sarcoma patients receiving interval compressed chemotherapy) and 21-day cycles (most others). Site will not be a stratification factor. Subjects will be randomized with equal allocation to each arm using a stratified block randomization scheme with varying block sizes (of size 2 - 4).

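### Adjusting the Cycle 1–2 co-primary comparison for G-CSF planned before randomisation would be a cheap gain in precision; the unadjusted test is valid without it

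*Combined protocol and SAP*

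**What the plan says.** Section 8.1 defines two co-primary endpoints. The one at issue is "a) the average day to recovery during Cycles 1 and 2", compared between arms. The other is the within-subject difference between genistein and placebo cycles.

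Section 8.2 gives the only named test for the between-arm comparison, a Mann-Whitney-Wilcoxon test without covariates: "Group sample sizes of 22 eligible subjects per group achieves approximately 80% power to detect a difference of 3 days with a 5% one-sided". The simulation behind it was run "assuming a null Poisson (mean 16.25) distribution and an alternative Poisson (mean 13.25) distribution", with no G-CSF component. Section 8.3 states: "Stratification will be based on the length of chemotherapy cycles". Site is expressly excluded, and no other factor is listed.

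G-CSF appears in four other places. Section 4.8.2 makes it a collected concomitant medication. Section 6.3 classifies it per cycle as "primary or secondary use (planned before the cycle began or in response to prolonged neutropenia, respectively". Section 7.2 makes its incidence a secondary endpoint. Section 8.4 compares its use by Cochran–Mantel–Haenszel statistics. Section 8.4 also mentions repeated measure models but names no covariate for any of them. The pre-treatment list in Section 6.2 covers G-CSF used in the previous 28 days and the anticipated anti-neoplastic regimen, but not G-CSF planned for the study cycles.

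**The concern.** G-CSF acts on the neutrophil count, so whether a subject is due to receive it from the start of a cycle is a plausible predictor of the day of recovery. If the arms differ by chance in how many subjects have such a plan, the Cycle 1–2 difference moves for a reason unrelated to genistein. If they do not differ, the mixture of users and non-users still widens the spread within each arm.

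The usual objection to adjusting for G-CSF is that its use may be a consequence of the outcome. That applies to reactive use. It does not apply to a plan fixed before the first dose of study supplement, which by the protocol's own definition precedes the cycle. A legitimate baseline covariate is therefore available and unused.

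**Working it through.** **1. The plan's own figure.** Inputs from Section 8.2: 22 per arm, Poisson means 16.25 and 13.25, one-sided 5% Mann-Whitney-Wilcoxon. Over 20,000 simulated trials, power is 80.2% with continuity correction and 80.5% without, which agrees with the stated 80%. The null rejection rate is 5.0%. Accrual also agrees: 44/0.9 = 48.9, against the stated 49–50.

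**2. Size of a chance imbalance.** Let p be the share with planned primary G-CSF and g the number of days by which it shifts recovery. Both are assumptions. Under simple 1:1 allocation the between-arm difference in share has SD = √(p(1−p) × 2/22), and the recovery difference moves by SD × g.

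| p | SD of imbalance | shift, g = 2 | shift, g = 4 |
|---|---|---|---|
| 10% or 90% | √(0.09 × 2/22) = 0.090 | 0.18 day | 0.36 day |
| 25% or 75% | √(0.1875 × 2/22) = 0.131 | 0.26 day | 0.52 day |
| 50% | √(0.25 × 2/22) = 0.151 | 0.30 day | 0.60 day |

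Against the 3-day target these shifts run from 0.18/3 = 6% to 0.60/3 = 20%.

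**3. Power if G-CSF spread comes on top of the Poisson variance.** The simulation was repeated with the planned-G-CSF factor added and the placebo mean held at 16.25. The unadjusted rank test was compared with rank ANCOVA on planned G-CSF, for a 3-day genistein effect.

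| p | g | unadjusted | adjusted | cost (points) |
|---|---|---|---|---|
| 25% | 2 | 77.9% | 79.1% | 1.2 |
| 50% | 2 | 77.0% | 78.9% | 1.9 |
| 75% | 2 | 78.2% | 79.3% | 1.1 |
| 25% | 4 | 72.9% | 78.7% | 5.8 |
| 50% | 4 | 70.9% | 79.2% | 8.3 |
| 75% | 4 | 73.3% | 78.6% | 5.3 |

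The type I error in these six settings is 4.8–5.1% unadjusted and 4.8–5.2% adjusted.

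**4. Power if the Poisson variance already contains that spread.** A normal approximation with mean variance (16.25 + 13.25)/2 = 14.75 gives Φ(3/√(14.75 × 2/22) − 1.645) = 82.8%. This should be compared only with figures from the same approximation. Adjustment removes p(1−p)g² from the variance. At p = 50%, g = 4 the residual variance is 14.75 − 4.0 = 10.75 and power becomes 91.8%. Across p = 25–75%, adjusted power is 84.5–85.0% for g = 2 and 89.6–91.8% for g = 4. In this case nothing stated is lost, and adjustment adds to it.

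**The case against.** **Randomisation already deals with it.** This stands. A reader might infer that the co-primary test is biased or has an inflated false-positive rate, but the results above do not support that. In the subset of simulated trials with at least 20 points more planned G-CSF in the genistein arm, the unadjusted false-positive rate is about 9–11% for a 2-day effect and 16–18% for a 4-day effect. An imbalance of that size in either direction arises in 11.0–17.5% of trials. Those rates are conditional on an unlucky draw in one direction, and averaged over all draws the rate is about 5%.

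**The added variance is not established.** This also stands. A reader might infer that the trial is underpowered. The mean of 16.25 comes from a chart review, and Section 8.2 does not say that G-CSF users were excluded. The variance follows from the Poisson choice, so the spread may already be inside it. The endpoint also averages two cycles, whereas the calculation uses a single Poisson count, which may offset part of any loss.

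**The magnitude is assumed.** It is. A 50% share is the worst case, and if planned G-CSF is nearly universal or rare the issue fades. Cycle-length strata may also balance regimen-driven plans in part; the documents do not say.

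**The crossover co-primary is protected.** Largely so. Eligible regimens repeat or alternate regularly (Section 3.1), so a constant plan cancels within subject. The point is confined to the Cycle 1–2 comparison.

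**The wider gap is the unspecified primary model.** It is true that Section 8.4 names no covariates at all, and regimen or age could be raised in the same way. Planned G-CSF has the advantage that it bears directly on the endpoint and that the protocol already distinguishes it from reactive use.

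**It may already be captured.** The eligibility worksheet is not set out in the protocol and the sample case report forms sit in the Procedure Manual, neither of which was available, so this cannot be checked.

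**Conclusion.** This is an optional improvement of low priority. The Cycle 1–2 comparison is neither stratified on nor adjusted for planned primary G-CSF, and it remains valid on average. Under the assumed ranges, a typical chance imbalance moves the estimate by roughly 0.2–0.6 day. The power at stake is about 1–8 points if G-CSF spread is additional to the planning variance. If it is not, the stated power stands and adjustment raises it somewhat. All of this rests on an assumed share and an assumed 2–4 day effect, with simple allocation in the simulation in place of stratified blocks. The documents supply neither the share nor the effect.

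**What to change.** Record before randomisation, as one yes/no item, whether primary G-CSF is planned for Cycles 1–2. For subjects already enrolled, use the Cycle 1 primary flag: by definition that plan predates the cycle, and the study supplement starts on Cycle 1 Day 1. Pre-specify this item as a single covariate alongside cycle length in the Cycle 1–2 analysis, for example by rank ANCOVA.

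Keep randomisation stratified by cycle length only, because a second factor would make four strata among 44 subjects. Do not adjust for secondary G-CSF, or for Cycle 2 plans made after randomisation, since both can be affected by the assigned supplement.

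The cost is one form item and one degree of freedom. The gain is small if planned G-CSF turns out to be nearly universal, rare, or determined by cycle length. The change concerns the analysis only and takes no position on when G-CSF should be given.
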